1.3.2. Drug Disposition Summary

The preclinical PK of INCB039110 was evaluated in rats, dogs, and monkeys. INCB039110 exhibits low-to-moderate systemic clearance, a low volume of distribution, and a short terminal elimination half-life. The oral bioavailability was low in monkeys (< 20%), moderate in dogs (43%), and high in rats (82%). INCB039110 is mainly cleared by metabolism and is a substrate

of CYP3A4 but does not significantly inhibit the activity of the major CYP enzymes, suggesting that the potential for INCB039110 to cause clinical drug-drug interactions through CYP inhibition is low.

1.3.3. Nonclinical Toxicology Summary

The toxicologic profile of INCB039110 was characterized in single- and multiple-dose oral studies of up to 3 months in duration in rats and dogs.

[REDACTED] Pharmacology-related clinical pathology and anatomical alterations in multiple-dose rat studies included a reversible lowering of white blood cell count, primarily because of a lower circulating lymphocyte count, and reversible lymphoid depletion in lymphoid tissues and reduction in bone marrow cellularity. [REDACTED]

In repeat-dose studies in dogs, gastrointestinal inflammation was determined to be the DLT.

[REDACTED] Clinical and histological evidence of JAK inhibition included decreased reticulocyte and/or lymphocyte counts, lymphoid depletion of lymphoid tissues, and/or reduction of bone marrow cellularity. [REDACTED]

INCB039110 was not genotoxic in the bacterial mutagenicity assay, the *in vitro* chromosome aberration assay in human lymphocytes, or the *in vivo* micronucleus assay in rats.

INCB039110 also did not demonstrate off-target activity nor was it active in a panel of approximately 60 non-JAK family kinases. Additional information on pharmacology, drug disposition, and nonclinical toxicology is available in the [INCB039110 IB](#).

1.3.4. Clinical Summary of INCB039110

INCB039110 has been administered as monotherapy in clinical studies to healthy subjects and subjects with rheumatoid arthritis, chronic plaque psoriasis, and myelofibrosis. INCB039110 is being administered in combination with gemcitabine and *nab*-paclitaxel to subjects with advanced solid tumors in an ongoing study (INCB 39110-116). INCB039110 has also been administered in combination with INCB040093 in subjects with B-cell malignancies. Additional information is available in the [INCB039110 IB](#).

1.3.5. Potential Risks of INCB039110

INCB039110 is known to affect the immune system; therefore an increased incidence of infections could occur. Strict clinical monitoring is indicated to identify and treat infections in study subjects should they occur, and a standard PJP prophylaxis regimen will be required for all

subjects receiving combination treatment with INCB050465 and INCB039110. Refer to the [INCB039110 IB](#) for further details.

INCB039110 has been shown to affect hematologic parameters. In a study of INCB039110 in subjects with myelofibrosis, anemia, and thrombocytopenia occurred in > 30% of the 87 subjects enrolled (refer to the [INCB039110 IB](#)). Subjects will have hematologic parameters closely monitored during this study.

Hyperlipidemia has previously been noted in subjects receiving JAK inhibitors ([Kontzias et al 2012](#)). Ten subjects (18.2%) were observed to have an increase in blood cholesterol greater than the upper limit of normal (ULN) after receiving combination treatment with INCB040093 and INCB039110 while enrolled in the INCB 40093-102 study. In the oncology population, monitoring and treatment of hyperlipidemia should be tailored as appropriate to individual subject characteristics, while exercising caution on study with cholesterol-lowering agents such as HMG-CoA reductase inhibitors that are associated with liver function abnormalities.

1.4. Overview of the Combination of INCB050465 and INCB039110

1.4.1. Nonclinical Pharmacokinetics and Drug Metabolism of the Combination

Both INCB050465 and INCB039110 are metabolized predominately by CYP3A4, but neither appears to be an inducer or inhibitor of CYP3A4 at clinically relevant concentrations. Also, INCB050465 is a P-gp inhibitor, while INCB039110 is a weak P-gp inhibitor. While both INCB050465 and INCB039110 are P-gp substrates, their efflux transport via P-gp is likely to be saturated at the doses proposed for clinical evaluation and thus further inhibition of P-gp should have no effect on INCB050465 or INCB039110 absorption. Therefore, a drug interaction between these compounds is unlikely in the setting of the proposed clinical study.

Pharmacokinetics will be evaluated in this study to evaluate potential effect of INCB040093 on INCB039110 PK, with evaluation of INCB050465 PK in combination with INCB039110 compared with INCB050465 monotherapy.

1.4.2. Clinical Summary of Combination Treatment with INCB050465 and INCB039110

As of 02 SEP 2016, 3 subjects had received the INCB050465 and INCB039110 combination therapy. No SAEs were reported for these 3 subjects, and no AEs led to study treatment discontinuation. Non-treatment-related AEs of spinal cord compression and pain led to study treatment interruption in 1 subject. Among these 3 subjects, 2 partial responses (PRs) were reported in Hodgkin lymphoma and mantle cell lymphoma (n = 1 each).

1.4.3. Clinical Summary of Combination Treatment With PI3K δ Inhibition (INCB040093) and JAK Inhibition (INCB039110)

Study INCB 40093-102 is an ongoing, open-label, dose escalation, safety and tolerability study of the PI3K δ inhibitor INCB040093 as monotherapy and in combination with INCB039110. As of 13 DEC 2015, 67 subjects had received treatment with the combination. No evidence of any impact on the PK of the INCB040093 from coadministration of INCB039110 was apparent ([INCB040093 IB](#)).

1.4.4. Potential Risks of Combination Therapy of INCB050465 and INCB039110

Incyte is proposing to study 2 investigational drugs INCB050465 and INCB039110 in combination for the treatment of relapsed/refractory B-cell malignancies. The principle toxicity of inhibiting both PI3K δ and JAK pathways is expected to be reversible effects on immune function. Combined inhibition may adversely affect both B cell and T cell immune function with resultant increased risk of a variety of infections. Subjects will be closely monitored for bacterial infections, viral reactivation, and opportunistic infections, and treatment will be interrupted for infections that can be easily managed with antibiotic therapy and discontinued for infections that are serious or require prolonged antibiotic therapy. Study INCB 40093-102 is combining another PI3K δ inhibitor, INCB040093 with INCB039110. The most frequently reported SAE in this study was PJP (5 subjects, 7.5%). The use of a standard Pneumocystis prophylaxis regimen is now mandated in subjects receiving combination therapy with INCB040093 and INCB039110. Since implementing this requirement, no additional cases of PJP have been observed in subjects receiving prophylaxis. Therefore, all subjects receiving combination therapy with INCB050465 and INCB039110 in this study must receive PJP prophylaxis. Viral reactivation (ie, shingles) was observed in subjects receiving INCB040093 monotherapy and combination therapy with INCB039110.

Effects on white blood cell, red blood cell, and platelet counts could result from JAK inhibition and result in infections, anemia, or thrombocytopenia requiring transfusions, which may be more likely in subjects with NHL that is refractory to recent therapy or transplantation.

INCB039110 has been shown to affect hematologic parameters; however, cytopenias are not expected to be worse with combination PI3K δ and JAK inhibition. In the study combining INCB039110 with INCB040093 as of 13 DEC 2015, anemia has occurred in 14.9% of subjects receiving combination therapy. Neutropenia has occurred in 28.4% of subjects receiving combination therapy; thrombocytopenia was reported in 31.3% of subjects receiving combination therapy (refer to the [INCB039110 IB](#)).

Combined inhibition is not expected to increase the risk of hepatic toxicity and liver function testing will be monitored regularly. Any hepatic toxicity is expected to be reversible. These potential risks are considered acceptable in a population with relapsed/refractory lymphoid malignancies.

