5.6. Dose Adjustment of Study Drug

5.6.1. Planned Dose Adjustments

Cohort dose escalation is described in Section 4.1. Intrasubject dose escalation of INCB050465 will be allowed during dose escalation, provided that the following criteria are met:

- The Protocol inclusion criteria are met.
- The subject has received 4 cycles of study drug and has not had a related or possibly related toxicity \geq Grade 2.
- The next dose level has been determined to be safe based on DLT rules (eg, no DLTs during Cycle 1).
- The subject is willing to submit to all visits and procedures as in Cycle 1 per the Protocol, except the PK [REDACTED] sampling will only be done as on Cycle 1 Day 15 (Day 1 and Day 8 PK [REDACTED] sampling will not be done).
- In the opinion of the investigator, the subject does not have any concurrent condition or circumstance that would complicate the dose escalation or PK sampling, or pose increased risk to the subject.
- The intrasubject dose escalation has been approved by the sponsor.

5.6.2. Criteria and Procedures for Dose Interruptions and Dose Reductions of INCB050465 and INCB039110

In some circumstances, it may be necessary to temporarily interrupt treatment as a result of adverse experiences that may have an unclear relationship to study drug. Treatment with INCB050465, the combination with INCB039110, or the combination with standard therapies may be delayed up to 2 weeks to allow for resolution of toxicity. If treatment needs to be interrupted in subjects receiving the combination of INCB050465 and INCB039110 for toxicities with unknown causality, both study medications should be held. However, based on the evolving experience with the study treatments, the suspected causal agent only may be held (while the other study treatment continues) until resolution of toxicity following consultation and approval with the medical monitor. Subjects may resume treatment if no medical condition or other circumstance exists that, in the opinion of the investigator, would make the subject unsuitable for further participation in the study. The treating investigator should contact the sponsor's medical monitor to discuss the case of any subject whose treatment has been delayed for more than 14 days before treatment with INCB050465 or the combination of INCB050465

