and INCB039110 may be restarted (see [Table 4](#)). Dose reductions of 1 or both (as applicable for subjects on combination therapy) study treatments may be necessary as described in [Table 4](#). For subjects who start on the 300 mg QD dose of INCB039110, the first dose reduction would be to 200 mg QD. If subjects start at a 200 mg QD dose of INCB039110, the combination of INCB050465 with INCB039110 at a lower dose (eg, 100 mg QD) will be subject to discussion with the sponsor. Alternatively, INCB039110 may be discontinued if dose reduction is indicated, and subjects may continue on INCB050465 monotherapy if they continue to receive benefit.

Because subjects may enter the study with extensive pretreatment and/or severe bone marrow infiltration by the primary disease, these dose-reduction rules are provided as guidelines. Individual decisions regarding dose reduction should be made using clinical judgment and in consultation with the sponsor's medical monitor, taking into account relatedness of the AE to the study drug and the subject's underlying condition. Subjects receiving dose reductions (but not meeting DLT criteria) during the first cycle will not be considered evaluable for the purposes of determining the MTD.

Table 4: Guidelines for Interruption and Restart of Study Drug

TOXICITY/NCI CTCAE GRADE	ACTION TAKEN
Chemistries:	

 Total bilirubin > 3.0 × ULN AST and/or ALT > 3.0 × ULN ALP ≥ 2.5 × ULN 
Note: For ALP increases in subjects with bone metastasis-related ALP elevation at baseline, contact sponsor to discuss clinical management and possible dose reductions.
	
Step 1: Interrupt study drug(s) up to 2 weeks (14 days) until the toxicity has resolved to ≤ Grade 1 except ALT/AST elevations, which may require 4 weeks (28 days) to resolve.
 
Step 2: Restart study drug(s) at next lower dose (or INCB050465 at 25% reduction if in expansion cohorts, rounded down to the nearest pill strength); monitor as clinically indicated.^a
 
Dose reductions may be made solely to the suspected agent if the causality can be reasonably assigned to that agent based on existing data (refer to the INCB050465 IB and INCB039110 IB) with approval of the medical monitor.

Hematologic:	

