Diarrhea/colitis (\geq Grade 2)	Step 1: Interrupt INCB050465. Perform work-up for infection (including CMV, C. difficile , etc). Initiate or continue supportive care (see Section 5.6.2.1). Consider colonoscopy with biopsy for \geq Grade 3. Step 2: If infection is ruled out, start oral steroids, or consider IV steroids if subject is being given IV fluids. If no improvement with oral steroids, switch to IV steroids. When diarrhea resolves to \leq Grade 1, continue supportive care and taper steroids over 4 weeks. When taper is complete and diarrhea is \leq Grade 1, restart INCB050465 at next lower dose in consultation with the medical monitor. If \geq Grade 2 diarrhea reoccurs, permanently discontinue INCB050465.
Pneumonitis (Grade 1)	Step 1: Interrupt INCB050465 until the toxicity has resolved. Step 2: Restart INCB050465 at next lower dose. Monitor as clinically indicated.
Pneumonitis (Grade \geq 2)	Permanently discontinue INCB050465.
Skin toxicity (eg, rash, pruritus, etc, unless otherwise specified) (Grade 2-3)	Step 1: Interrupt INCB050465 until the toxicity has resolved to \leq Grade 1. Step 2: Restart INCB050465 at same dose. If assessed as related to INCB050465, restart at next lower dose in consultation with the medical monitor.
Exfoliative dermatitis (Grade 1)	Step 1: Interrupt INCB050465 until the toxicity has resolved. Step 2: Restart INCB050465 at next lower dose. Monitor as clinically indicated.
Exfoliative dermatitis (\geq Grade 2)	Permanently discontinue INCB050465.
Intestinal perforation (any grade)	Permanently discontinue INCB050465.
Pneumocystis jiroveci pneumonia infection	Interrupt INCB050465. Permanently discontinue INCB050465 if Pneumocystis jiroveci pneumonia infection is confirmed.
CMV infection	Subjects with CMV viremia without associated clinical signs of CMV infection should be carefully monitored. Consider interrupting INCB050465 for subjects with CMV viremia and clinical signs of infection until the infection has resolved. Restart INCB050465 reduced by 1 dose level if approved by the medical monitor.
Varicella zoster infection	Interrupt INCB050465. Restart INCB050465 only by approval of the medical monitor.
Any Grade 1 or 2 toxicity unless otherwise specified	Continue study drug treatment(s); monitor as clinically indicated.

Table 4: Guidelines for Interruption and Restart of Study Drug (Continued)

TOXICITY/NCI CTCAE GRADE	ACTION TAKEN

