Any Grade 2 or 3 toxicity, if clinically significant and not manageable by supportive care unless otherwise specified	
Step 1: Interrupt study drug(s) up to 2 weeks (14 days) until toxicity resolves to \leq Grade 1 or medical monitor approval.
 
Step 2: Restart study drug(s) at next lower dose for events considered to be drug-related (or 25% reduction if in expansion cohort, rounded down to the nearest pill strength); monitor as clinically indicated.^a
 
Dose reductions may be made solely to the suspected agent if the causality can be reasonably assigned to that agent based on existing data (refer to the INCB050465 IB and INCB039110 IB) with approval of the medical monitor.

Any recurrent Grade 2 or 3 toxicity after 2 dose reductions	Discontinue study drug treatment(s) and follow-up per Protocol.
Any other Grade 4 toxicity	Discontinue study drug(s) and follow-up per Protocol. However, if toxicity resolves to \leq Grade 1 within 2 weeks, may restart treatment at 1 dose level lower with medical monitor approval.

CMV = cytomegalovirus; IV = intravenous.

^a Note: Only 2 dose reductions due to AEs are permitted.

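### For subjects on INCB050465 plus INCB039110, Table 4's CMV and zoster rows cover INCB050465 only and do not fit Sections 5.6.2 and 1.4.4

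*Protocol*

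**What the plan says.** Section 1.4.4 of the protocol sets out the risks of the INCB050465 plus INCB039110 pair. It names bacterial infection, viral reactivation and opportunistic infection. It then gives two responses: treatment is interrupted when an infection is easily managed, and "discontinued for infections that are serious or require prolonged antibiotic therapy".

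Section 5.6.2 gives the general rule for combination subjects whose treatment has to be interrupted: "for toxicities with unknown causality, both study medications should be held". As an alternative, "the suspected causal agent only may be held (while the other study treatment continues) until resolution of toxicity following consultation and approval" from the medical monitor. The same section says that "these dose-reduction rules are provided as guidelines". It also gives an INCB039110 step for subjects who start at 300 mg QD: "the first dose reduction would be to 200 mg QD".

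Table 4, in the same section, has separate rows for two viral infections:

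- **CMV.** Viremia without clinical signs is monitored. Otherwise: "Consider interrupting INCB050465 for subjects with CMV viremia and clinical signs of infection until the infection has resolved". INCB050465 may then restart one dose level lower if the medical monitor approves.
- **Varicella zoster.** INCB050465 is interrupted, followed by: "Restart INCB050465 only by approval of the medical monitor".

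Neither row mentions INCB039110, and neither separates serious from non-serious infection.

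**The concern.** Infection is the harm that Section 1.4.4 links most directly to combined inhibition. It reports shingles with the related PI3K-delta inhibitor INCB040093, both alone and with INCB039110. Section 1.3.5 gives INCB039110 an infection risk of its own. When a virus reactivates in a subject taking both drugs, the site needs to know what to do with each of them.

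The two rows answer for one drug only. An investigator who goes straight to the zoster row finds a single-agent hold and no reminder that 5.6.2 requires approval for one. An investigator who goes to the CMV row may reasonably decide not to interrupt at all. In either case a subject with active viral disease could stay on the JAK1 inhibitor without the decision that the 5.6.2 text intends. After a short but serious infection, the rows lead towards restart while 1.4.4 says to discontinue.

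Clear hold instructions also matter more under Amendment 10. Ongoing subjects then self-administer between visits up to 12 weeks apart (Section 7.10.1), and safety assessments are left to the investigator's discretion (Section 7.4).

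**Working it through.** No formula applies to the main question, so the check compares the texts. One small count gives the scope.

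**1. The infection-triggered rows of Table 4.** There are four.

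| Row | Drug acted on | Outcome |
|---|---|---|
| Neutropenia with Grade 3 or higher infection | Study drug(s) | Interrupt, restart lower |
| Confirmed PJP | INCB050465 | Permanent stop; 5.6.3 then withdraws the subject from the study |
| CMV | INCB050465 | Interruption optional if symptomatic; restart lower with approval |
| Zoster | INCB050465 | Interrupt; restart with approval |

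Only CMV and zoster act on INCB050465 alone and also allow restart.

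**2. Zoster row against 5.6.2.** Section 5.6.2 holds both drugs if causality is unknown, and one drug if a causal agent is suspected and the medical monitor approves. The zoster row goes directly to an INCB050465 hold. Its approval step concerns restart, not the decision to leave INCB039110 running. Read literally, it permits what 5.6.2 allows only with approval.

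**3. CMV row against 5.6.2.** The hold-both default applies when treatment needs to be interrupted. For symptomatic CMV the row asks only that interruption be considered. If the investigator does not interrupt, the default does not start, and no instruction about INCB039110 is reached.

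**4. Both rows against 1.4.4.** Section 1.4.4 discontinues for serious infection. Both rows allow INCB050465 to restart with medical monitor approval at any level of seriousness.

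**5. What other rules remove from that conflict.**

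- Section 5.6.3 makes a toxicity that delays therapy by more than 14 days a permanent-discontinuation criterion unless the medical monitor approves otherwise. This covers most of the prolonged cases.
- Section 5.6.3 also requires a stop for a related event judged contrary to the subject's interest. Section 5.7.1 requires withdrawal when the investigator judges that continuing would harm the subject.
- What is left is serious CMV or zoster that resolves within 14 days and that nobody has judged unsuitable for continuation.

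**6. Scope.** Section 9.2 plans about 12 subjects in Part 2, and Table 1 allows up to 15 in Cohort E. 12 + 15 = 27, and 27/150 = 18% of the approximate total. Subjects who cross over to this combination under Section 4.2.5 are additional.

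**The case against.** The strongest reply is that the protocol already controls this. Table 4 serves the monotherapy and combination parts together, and naming INCB050465 alone is its habit across the event-specific rows. Section 5.6.2 supplies the combination rule. Attribution of a viral reactivation will often be uncertain, which is exactly when 5.6.2 holds both drugs. Both rows require medical monitor approval before INCB050465 restarts. Serious events reach the sponsor within 24 hours with relatedness assessed for each drug (Section 8.3.2). Section 1.4.4 is a risk narrative in the introduction, and its reference to antibiotics suits viral disease poorly.

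Much of this stands, and it rules out several stronger readings that a reader might infer:

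- *That the protocol tells sites to continue INCB039110 through viral infection.* It does not. The rows are silent, and 5.6.2 still applies once treatment is interrupted.
- *That restart of INCB050465 is uncontrolled.* Approval is required in both rows.
- *That every serious or prolonged infection conflicts with 1.4.4.* Step 5 of the working narrows this to short, serious CMV or zoster. Restart after non-serious zoster is consistent with 1.4.4.
- *That the neutropenic-infection row has the same defect.* It acts on study drug(s), and 5.6.2 already directs that individual dose-reduction decisions be made in consultation with the medical monitor.
- *That the zoster row must state an INCB050465 restart dose.* Leaving the dose to the approving medical monitor is a defensible choice.
- *That the general row, for "Any Grade 2 or 3 toxicity, if clinically significant and not manageable by supportive care unless otherwise specified", certainly excludes zoster.* The exception could mean specified for INCB050465 only, which would leave that row governing INCB039110. The wording does not settle it, and the point does not depend on it.

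Three things are not answered. The zoster row omits an approval that 5.6.2 requires. The optional CMV hold can bypass the default. And although 1.4.4 is introductory, it names viral reactivation, and its word for serious infection is not tied to antibiotics. The guideline status in 5.6.2 gives latitude on dose reductions, but it does not explain why one of two immunosuppressive drugs is left out of an infection row.

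**Conclusion.** The point holds in a limited form. For Part 2, Cohort E and crossovers to that combination, the CMV and zoster rows address one of the two drugs. They are inconsistent with 5.6.2 on how a single-agent hold is decided, and with 1.4.4 for serious CMV or zoster that resolves within 14 days. It should be corrected, because the inconsistency concerns the main expected risk of the pair and is cheap to remove.

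The scope is about 27 planned subjects, 18% of about 150, before crossovers. A reader might take 27 as the number who would be affected; it is not. The documents give no CMV or zoster rate for this pair, and they do not say how many subjects remain on it. Section 1.4.2 records 3 combination subjects as of 02 SEP 2016.

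The conclusion assumes that some sites will act on the specific row without returning to the general text of 5.6.2. Confidence is medium: a site that reads 5.6.2 in full would reach the intended handling in many cases.

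**What to change.** By protocol amendment, for subjects receiving INCB050465 plus INCB039110:

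1. Change the symptomatic-CMV and zoster rows of Table 4 to: *Interrupt INCB050465 and INCB039110; hold one agent alone only with medical monitor approval under 5.6.2; restart of either drug needs medical monitor approval.* Any INCB039110 reduction follows the existing step from 300 to 200 mg QD.
2. Have Section 1.4.4 refer to Table 4 and state that restart after a serious infection is an exception needing medical monitor approval.

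Holding both is the better default because both drugs carry infection risk and 5.6.2 already does this when causality is unclear. The approved single-agent hold stays available. For symptomatic CMV the change does replace an optional hold with a required one, which is a clinical decision for the sponsor to confirm.

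The cost is two edited rows and one cross-reference, with no new data collection. Some combination subjects would have a short additional INCB039110 interruption.
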